injector(s) should have no other contact with the participant during the study, should not discuss the participant's treatment with the participant, participant's caregiver, or other site personnel at any time, and will not be permitted to review the participant's medical records, questionnaires, or the electronic CRF prior to each injection. The designated injector(s) should be documented in the source documents at each visit.

Study treatment will be administered weekly in the clinic for 31 weeks with weekly office visits for 32 weeks. Patients will remain at the study site for a minimum of 30 minutes (+/- 10 minutes) after injections at weeks 0, 1, 2, 16, 17 and 18 injections for safety monitoring.

During the 32-week treatment period, patients will attend weekly clinical study visits. Clinical assessments, collection of samples for bermekimab concentrations, and safety testing will be performed at specified clinic visits. After completion of the 36-week study period, data will be locked and analyzed for safety and efficacy endpoints for all arms. In addition to the analyses that will be performed following the formal database lock at the end of the study at Week 36, an additional database lock may be performed at Week 16, and interim analyses utilizing unblinded efficacy data available as the study progresses, may also be conducted to help plan potential future development activities. An internal interim analysis committee (IAC) will be established to review the interim data and formulate recommended decisions/actions. The IAC will consist of at least a clinician and a statistician (neither of whom are involved in study conduct or compound development), one of whom will chair the committee, and may also include other members as required by the nature of the IAs. Details will be provided in a separate IAC charter, which will define the organization and roles and responsibilities of the committee, possible recommendations or requests, and the communication process following IA reviews. Results from the Week 16 database lock and/or interim analyses will not be disseminated to investigators or subjects participating in the study. In addition, results of the interim analyses will not be disseminated to individuals associated with the conduct of the study.

Patients will be monitored at a follow up visit (visit 34/week 36) for safety and clinical assessments after completing the 32 week treatment period.

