## **5. TREATMENT PLAN**

### **5.2 STUDY PROCEDURES**

#### **PLACEBO-CONTROLLED PERIOD**

**Screening (maximum 30 days): The screening period begins once the informed consent is signed.**

- Informed Consent
- Inclusion/ Exclusion
- Demographics
- Medical History
- Concomitant Medications/Treatments
- Physical Exam
- Electrocardiogram
- Vital Signs (blood pressure, pulse, oxygen saturation, respiratory rate and body temperature)
- Height
- Weight
- Body Mass Index (BMI) [BMI= weight (kg)/height (m^2)]
- Patient Diary
- Patient Oriented Eczema Measure (POEM)
- Hospital Anxiety and Depression Scale (HADS)
- Dermatology Life Quality Index (DLQI)
- Investigator's Global Assessment (IGA)
- Eczema Area and Severity Index (EASI)
- Global Individual Signs Score (GISS)
- SCORing Atopic Dermatitis (SCORAD)
- Body Surface Area (BSA) involvement with atopic dermatitis (must be greater than 10%)
- Urinalysis: pH, protein, glucose and blood cells (RBCs and WBCs)
- Blood Draw:

- Chemistry panel: Albumin, Alkaline Phosphatase, ALT, AST, GGT, Bicarbonate (CO2), Calcium, Chloride, Creatinine, Glucose, Potassium, Sodium, Total Bilirubin, Total Protein, Urea Nitrogen
- Hematology Panel: Complete Blood Count (CBC) with differential and platelets
- Infectious disease screening: HIV antibody, Hepatitis C antibody, Hepatitis B panel (HBsAg, anti-HBc, anti-HBs), and interferon gamma release assay (IGRA)
- Serum pregnancy test for WOCBP
- Inflammation Markers: CRP (C-Reactive Protein), ESR (Erythrocyte Sedimentation Rate)
- Randomization to study arm (once confirmed patient has passed screening requirements).

\*\*\*Patients will be monitored at the study site at visits 1, 2, 3, 17, 18 & 19 (weeks 0, 1, 2, 16, 17 & 18) for a minimum of 30-minutes after study drug administration. Vital signs and AE assessments will be done at 30 minutes (+/- 10 minutes) post-injection.\*\*\*

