## **7. ASSESSMENT OF SAFETY**

Safety will be assessed by monitoring adverse events, vital signs, physical examinations, ECG, and clinical laboratory measurements. Data from ECG will be included in safety analysis only when all of these measures are available for each subject (baseline and last visit). Adverse events will be monitored from visit 1 (post-injection) through visit 34 (week 36). Any serious adverse events whether related to study drug or not will be followed up until resolution.

Study drug, bermekimab, will be administered under close observation in a facility equipped to handle anaphylaxis or injection site reactions. Subjects must be closely monitored at the study site at visits 1, 2 and 3 (for the first three injections) until at least 30 minutes following the administration of the antibody. Vital signs and AE assessments will be done at 30 minutes (+/- 10 minutes) post-injection.

Any grade 3 or greater injection site reaction must be reported to the sponsor within 24 hours of learning of the event.

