The mechanism behind infusion or injection site reactions is not well understood. In some cases, it may involve a reaction against the antibody products themselves, particularly where the primary sequence of the antibody has been modified *in vitro* or is derived from non-human system or, against some minor residual component from the manufacturing process (i.e. host cell proteins). Bermekimab is derived from and has undergone immunological selection in humans, thus anti-bermekimab responses are highly unlikely. To date, there has been a very low incidence of injection site or infusion reactions observed (27 patients out of 911 total; 3.0%). In order to mitigate this class-specific risk, close monitoring is required during the bermekimab infusion/ injection and for at least 30 minutes after the end of the infusion/ injection for the first 3 doses. Availability of resuscitation equipment must be ensured although this has never been used for any patient in any of our studies. Pre-medication with antihistamines, NSAIDs or corticosteroids is not required but allowed at PI's discretion.

An expanded discussion of potential risks and monitoring with bermekimab therapy is located in Section 4.6 of the Investigator's Brochure.

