## **COVID-19 APPENDIX**

### **GUIDANCE ON STUDY CONDUCT DURING THE COVID-19 PANDEMIC**

It is recognized that the Coronavirus Disease 2019 (COVID-19) pandemic may have an impact on the conduct of this clinical study due to, for example, self-isolation/quarantine by patients and study-site personnel; travel restrictions/limited access to public places, including hospitals; study site personnel being reassigned to critical tasks.

In alignment with recent health authority guidance, the sponsor is providing options for study-related patient management in the event of disruption to the conduct of the study. This guidance does not supersede any local or government guidelines or requirements or the clinical judgement of the investigator to protect the health and well-being of patients and site staff. If, at any time, a patient's safety is considered to be at unacceptable risk, drug product will be discontinued, and study follow-up will be conducted.

Scheduled visits that cannot be conducted in person at the study site will be performed to the extent possible remotely/virtually or delayed until such time that on-site visits can be resumed. At each contact, patients will be interviewed to collect safety data. Key efficacy endpoint assessments should be performed if required and as feasible. Patients will also be questioned regarding general health status to fulfill any physical examination requirement.

Every effort should be made to adhere to protocol-specified assessments for patients on drug product, including follow up. Modifications to protocol-required assessments may be permitted via COVID-19 Appendix after consultation between the patient and investigator, and with the agreement of the sponsor (see below).

The sponsor will continue to monitor the conduct and progress of the clinical study, and any changes will be communicated to the sites and to the health authorities according to local guidance. If a patient has tested positive for COVID 19, the investigator should contact the sponsor's responsible medical officer to discuss plans for drug product and follow-up. Modifications made to the study conduct as a result of the COVID-19 pandemic should be summarized in the clinical study report.

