**ADDITIONAL ELEMENTS, WHERE APPLICABLE:**

- Certain protocol-mandated visits to the study site may not be possible during the COVID-19 outbreak. Therefore, temporary measures may be implemented if considered appropriate by the sponsor and investigator to maintain continuity of patient care and study integrity. Certain measures, such as those listed below, may be necessary and should be instituted in accordance with applicable (including local) laws, regulations, guidelines, and procedures:
  - remote (eg, by phone / telemedicine) or in-person, off-site (eg, in-home) interactions between site staff (or designees) and patients for study procedures e.g. those related to safety monitoring / efficacy evaluation / drug product storage and administration (including training where pertinent)
  - procurement of drug product by patients (or designee) or shipment of drug product from the study site directly to patients for at home administration (including the potential for self-administration of drug product)
  - laboratory assessments using a suitably accredited local laboratory; for selected measures (eg, urine pregnancy), home testing may be employed
  - other procedures, eg, imaging, may be conducted at an appropriate facility
- Missed assessments/visits will be captured in the case report form (CRF) for protocol deviations. Discontinuations of drug products and withdrawal from the study should be documented with the prefix “COVID-19-related” in the CRF.
  - other relevant study data elements impacted by the pandemic should also be documented / labeled as “COVID-19-related” in CRFs and / or other study systems, as directed by detailed sponsor guidance. These may include missed / delayed / modified study visits / assessments / dosing, and instances where temporary measures such as those above are implemented.
- The sponsor will evaluate the totality of impact of COVID-19 on collection of key study data and additional data analyses will be outlined in study SAP(s).
- Precaution: for those who may carry a higher risk for severe COVID-19 illness (eg, those aged over 65 years), follow guidance from local health authorities when weighing the potential benefits and risks during participation in the study.

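### The protocol's lists of visits needing 30-minute on-site observation conflict, so Arm 3's first bermekimab doses can be read as unmonitored; the COVID-19 appendix does not except those doses from home self-injection

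*Protocol*

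**What the plan says.** Section 7 of the protocol sets a general condition on dosing: "Study drug, bermekimab, will be administered under close observation in a facility equipped to handle anaphylaxis or injection site reactions". It then limits the 30-minute observation: "Subjects must be closely monitored at the study site at visits 1, 2 and 3 (for the first three injections").

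Two other places give a longer list. The synopsis (Trial Design) keeps patients on site for at least 30 minutes "after injections at weeks 0, 1, 2, 16, 17 and 18 injections for safety monitoring". Section 5.2, Study Procedures, at the end of the screening list, names "visits 1, 2, 3, 17, 18 & 19 (weeks 0, 1, 2, 16, 17 & 18").

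Footnote 2 of calendar 5.2.1 names visits 1 to 3 only. Footnote 2 of calendar 5.2.2 names visits 1, 2, 3, 17, 18 and 19 but gives the last three as Weeks 18, 19 and 20.

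Section 9.7 gives the reason for observation. To mitigate the class risk of injection reactions, it requires close monitoring during "the bermekimab infusion/ injection and for at least 30 minutes after the end of the infusion/ injection for the first 3 doses". It adds: "Availability of resuscitation equipment must be ensured although this has never been used for any patient in any of our studies".

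Arm 3 receives its first bermekimab at visit 17 (Week 16) and remains blinded (calendar 5.2.1, footnote 7).

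The COVID-19 appendix lists, among measures that the sponsor and investigator may adopt, "shipment of drug product from the study site directly to patients for at home administration (including the potential for self-administration of drug product"). Visits that cannot take place on site are to be "performed to the extent possible remotely/virtually or delayed until such time that on-site visits can be resumed".

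**The concern.** The protocol's stated protection against injection reactions is observation of the first three bermekimab doses. For Arms 1 and 2 these doses begin at Week 0. For Arm 3 they fall at Weeks 16, 17 and 18, after 16 weekly dosing visits (Weeks 0 to 15) at which only placebo was given. Section 7 is where a site would look for the safety rule, and its list stops before Arm 3 has received any drug. The calendar that contains the Week 16 column omits Week 16 from its footnote.

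The appendix is a second route to the same gap. Home self-administration is permitted, no dose is excepted, and no observation or equipment condition is attached to a home dose. The investigator is blinded, so case-by-case judgement at Week 16 cannot pick out the patients who are starting drug.

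What is at stake is patient safety at a small number of identifiable doses. The primary efficacy analysis is not affected.

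**Working it through.** No power or error-rate calculation applies. The check compares the texts and does some counting.

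**Step 1: compare the lists.** The reference is Section 5.2, Study Procedures.

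| Place in protocol | Visits | Weeks | Against Weeks 0, 1, 2, 16, 17, 18 |
|---|---|---|---|
| Section 5.2, Study Procedures | 1, 2, 3, 17, 18, 19 | 0, 1, 2, 16, 17, 18 | reference |
| Synopsis, Trial Design | not numbered | 0, 1, 2, 16, 17, 18 | identical |
| 5.2.1, footnote 2 | 1, 2, 3 | 0, 1, 2 | omits 16, 17, 18 |
| Section 7 | 1, 2, 3 | not stated | omits 16, 17, 18 |
| 5.2.2, footnote 2 | 1, 2, 3, 17, 18, 19 | 0, 1, 2, 18, 19, 20 | visits right; weeks omit 16 and 17, add 19 and 20 |

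Two lists agree, two omit the second block, and one misdates it. The visit days settle which weeks are right: visits 17, 18 and 19 fall on Days 112, 119 and 126, and 112/7 = 16, 119/7 = 17, 126/7 = 18.

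**Step 2: patients concerned.** With about 90 patients randomized 1:1:1, Arm 3 has about 90/3 = 30, and Arms 1 and 2 together about 90 − 30 = 60.

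**Step 3: the appendix against the six observed visits.** The home-dosing text names no visit or dose as an exception. All the observed visits except Weeks 17 and 18 include severity scoring and blood draws (Section 5.2), and Week 0 also needs eligibility re-verification. Weeks 17 and 18, Arm 3's second and third bermekimab doses, have neither scoring nor a blood draw. They would therefore be the simplest of the six to move home. This is an inference; the documents do not say how many doses were moved.

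**Step 4: how often a reaction might occur.** Section 9.7 reports 27 patients with infusion or injection-site reactions out of 911: 27/911 = 2.96%, which agrees with the stated 3.0%. If that rate carried over to 30 patients, the expected number would be 30 × 0.0296 = 0.89, and the chance of at least one would be 1 − (1 − 27/911)^30 = 0.59. The rate pools intravenous and subcutaneous use and is not limited to first doses or serious events, so it is context only.

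**Step 5: what a dosing rule would cost in data.** PK samples are scheduled at Weeks 0, 1, 2, 3, 4, 5, 8, 12, 16, 24, 32 and 36, 12 in all. SAP 7.1.1.1 drops concentrations at and after a visit dosed outside ±3 days. A late Week 16 dose therefore loses 4 samples (16, 24, 32, 36), and a late Week 17 or 18 dose loses 3. A late Week 1 or 2 dose loses 11 or 10, but only in Arms 1 and 2, because SAP 7.1 does not summarise Arm 3's PK before Week 16.

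There are 32 dosing visits (Weeks 0 to 31). Protecting six leaves 32 − 6 = 26 open to unsupervised home dosing; 6/32 = 19%.

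**The case against.** **The list conflict is clerical.** Two lists are correct, the 5.2.2 calendar's own columns show visit 18 as Week 17 and visit 19 as Week 18, and Section 9.7 covers the first three bermekimab doses whatever the visit number. This stands in part: a site that reads the whole protocol would probably observe Weeks 16 to 18. A reader might infer that Arm 3's first doses would go unobserved as a matter of plan, and the documents do not support that. But Section 9.7 does not say when those doses occur, and a blinded site cannot work it out patient by patient. Section 7's parenthesis about the first three injections points, for Arm 3, to placebo.

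**The appendix already protects patients.** A reader might infer that it waives first-dose observation. It does not. Sites are to make every effort to keep protocol assessments, and the 30-minute check is one of these. Changes need the sponsor's agreement, drug is discontinued if risk is judged unacceptable, and staff-attended home visits and delay are both offered. All of this stands, and the gap exists only because the text is silent. What remains is that none of these safeguards is tied to first doses or to equipment at home.

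**Blinding adds little.** The correct lists apply observation to every arm, so no one needs to know who is in Arm 3. This is right, and it is the reason for a rule that applies to all arms alike.

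**Conclusion.** The concern holds as a conflict between monitored-visit rules, with a secondary gap in the COVID-19 appendix. Three of five lists omit or misdate Weeks 16 to 18. Read alone, Section 7 or footnote 2 of 5.2.1 would leave the first bermekimab doses of about 30 of 90 patients without the protocol's own mitigation, even with no pandemic disruption. The appendix point is weaker because it rests on the absence of an exception.

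The documents do not support a count of patients left unobserved or any claim that harm is likely. Past reactions were infrequent and resuscitation equipment has never been used, so few serious events are expected. The correction is modest but worth making because it is cheap and preserves the blind.

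Assumptions: equal arms of about 30, and no restriction on home dosing at these visits in the sponsor guidance or procedures that the appendix refers to but that are not in these documents.

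**What to change.** In the protocol:

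1. Section 7: replace the reference to visits 1 to 3 and its parenthesis with *visits 1, 2, 3, 17, 18 and 19 (Weeks 0, 1, 2, 16, 17 and 18)*.
2. Calendar 5.2.1, footnote 2: add visit 17 (Week 16).
3. Calendar 5.2.2, footnote 2: change Weeks 18, 19 and 20 to 16, 17 and 18.
4. COVID-19 appendix, for all arms: *Doses at Weeks 0, 1, 2, 16, 17 and 18 are given on site, or off site by qualified staff with at least 30 minutes of observation and resuscitation equipment available. Otherwise the dose is delayed, and the sponsor is contacted about rescheduling if the delay exceeds 3 days.*
5. Section 7, equipped-facility sentence: add *except for home doses at other visits permitted under the COVID-19 appendix*. Without this, the sentence still contradicts home dosing at the other 26 visits.

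Optionally, extend the 30-minute injection-site reaction summary in SAP 6.1, now Weeks 0 to 2, to Weeks 16 to 18. This may need an eCRF field.

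The cost falls during disruption. Doses at Weeks 16 to 18 may be delayed or missed in every arm, including about 60 Arm 1 and 2 patients well past their first doses. Delay has little room: the Week 16 window ends on Day 115 (112 + 3) and the Week 17 window opens on Day 116 (119 − 3), so a delay of more than 3 days runs into the next dose. Some by-visit PK data would be lost, as counted above. A missed dose before Week 16 removes a patient still on treatment from the per-protocol set (SAP 2.4.1.2). A missed Week 16 dose removes an Arm 3 patient from the post-Week 16 efficacy summaries (SAP 5.2.3 and 5.4). A late dose recorded as Week 16 should keep that patient in, since SAP 2.2 uses nominal visits, but this is an inference. EASI is scored before the Week 16 injection, so delaying only the injection leaves the primary endpoint untouched.

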## **8. STUDY VARIABLES**

### **8.1 DEMOGRAPHIC AND DISEASE CHARACTERISTICS**

Demographic characteristics will include standard demography (age, sex, race, weight, and BMI) medical history, medication history, and prior biologic use for each patient. Characteristics of the patient's atopic dermatitis, including duration of disease, baseline EASI score (including individual signs score), baseline Investigator's Global Assessment, baseline body surface area involvement, baseline pruritus numerical rating score, baseline SCORAD score, baseline patient-oriented eczema measure, baseline DLQI, and baseline HADS score, will be collected. Baseline is defined as the week 0 (visit 1), pre-injection assessment.

### **8.2 STUDY ASSESSMENTS**

- **Eczema Area and Severity Index**

The EASI is a validated measure used in clinical practice and clinical trials to assess the severity and extent of AD. Four AD disease characteristics will be assessed for severity by the investigator or designee on a scale of "0" (absent) through "3" (severe). In addition, the area of AD involvement will be assessed as a percentage by body area of head, trunk, arms, and legs and converted to a score of 0 to 6.

- **Investigator's Global Assessment**

The IGA is an assessment scale used in clinical studies to determine severity of AD and clinical response to treatment based on a 5-point scale ranging from 0 (clear) to 4 (severe).

- **Global Individual Signs Score**

Individual components of the AD lesions (erythema, infiltration/papulation, excoriations, and lichenification) will be rated globally (ie, each assessed for the whole body, not by anatomical region) on a 4-point scale (from 0=none to 3=severe) using the EASI severity grading criteria.

- **SCORing Atopic Dermatitis**

The SCORAD is a validated tool used in clinical research and clinical practice that was developed to standardize the evaluation of the extent and severity of AD. There are 3 components to the assessment: A = extent or affected body surface area, B = severity, and C = subjective symptoms. The extent of AD is assessed as a percentage of each defined body area, and reported as the sum of all areas, with a maximum score of 100% (assigned as "A" in the overall SCORAD calculation). The severity of 6 specific symptoms of AD (redness, swelling, oozing/crusting, excoriation, skin thickening/ lichenification, dryness) is assessed

using the following scale: none (0), mild (1), moderate (2), or severe (3) (for a maximum of 18 total points, assigned as “B” in the overall SCORAD calculation). Subjective assessment of itch and sleeplessness is recorded for each symptom by the patient or relative on a VAS, where 0 is no itch (or sleeplessness) and 10 is the worst imaginable itch (or sleeplessness), with a maximum possible score of 20. This parameter is assigned as “C” in the overall SCORAD calculation. The SCORAD is calculated as:  $A/5 + 7B/2 + C$  where the maximum is 103.

Body surface area affected by AD will be assessed for each section of the body (the possible highest score for each region is: head and neck [9%], anterior trunk [18%], back [18%], upper limbs [18%], lower limbs [36%], and genitals [1%]) and will be reported as a percentage of all major body sections combined. Body Surface Area (BSA) will be extracted using SCORAD.

- **Numerical Rating Scale (NRS) for Pruritus & Pain**

Patients will be given a diary to complete each night before bed. Patients will be asked to report “average pain”, and “worst moment pain” as well as “average itch” and “worst moment itch” on a 0-10 numeric rating scale. Patient diaries will be collected weekly.

- **Patient Oriented Eczema Measure**

The POEM is a 7-item, validated questionnaire used in clinical practice and clinical trials to assess disease symptoms in children and adults. The format is a response to 7 items (dryness, itching, flaking, cracking, sleep loss, bleeding, and weeping) based on frequency during the past week (ie, 0 = no days, 1 = 1 to 2 days, 2 = 3 to 4 days, 3 = 5 to 6 days, and 4 = all days) with a scoring system of 0 to 28; the total score reflects disease-related morbidity. The POEM is provided in the study reference manual.

- **Hospital Anxiety and Depression Scale**

The HADS is an instrument for screening anxiety and depression in non-psychiatric populations; repeated administration also provides information about changes to a patient’s emotional state. The HADS consists of 14 items, 7 each for anxiety and depression symptoms; possible scores range from 0 to 21 for each subscale. The following cut-off scores are recommended for both subscales: 7 to 8 for possible presence, 10 to 11 for probable presence, and 14 to 15 for severe anxiety or depression. The HADS is provided in the study reference manual.

- **Dermatology Life Quality Index**

The DLQI is a 10-item, validated questionnaire used in clinical practice and clinical trials to assess the impact of AD disease symptoms and treatment on QOL. The format is a simple response (0 to 3 where 0 is “not at all” and 3 is “very much”) to 10 questions, which assess QOL over the past week, with an overall scoring system of 0 to 30; a high score is indicative of a poor QOL. The DLQI is provided in the study reference manual.

- **Pharmacokinetics (PK) and Interleukin-6 (IL-6)**

An enzyme-linked immunosorbent assay (ELISA) has been developed to specifically measure bermekimab levels in human plasma. Blood will be drawn into three 6 ml collection tubes at each research draw collection time point as outlined in section 5. These samples will be collected per the study lab manual and shipped to the Sponsor for PK and IL-6 analyses. The samples will also be used for various pharmacodynamic (PD), biomarker, and general research analyses. The PK samples will also be used to test for the presence of antibodies against bermekimab. The IL-6 samples will be used to test for change in serum IL-6 levels in patients, which has shown to correlate with disease severity in HS and potentially a more reliable predictor of treatment response in HS patients than CRPxvii, xviii.

